8.4 Analysis of primary endpoint

The probability of PSA-progression-free survival over time will be estimated using the Kaplan-Meier method and shown with 80% pointwise confidence limits. The six-month PSA-progression-free survival will be compared to the null-value of 50% using a z-test at a one-sided 10% significance level.

8.5 Analysis of secondary endpoints

The PSA nadir values will be summarized with mean and standard deviation as absolute values and as percent change from baseline PSA value. The time to PSA nadir and time to subsequent antineoplastic therapy will be summarized using Kaplan-Meier (KM) curves. The median will be estimated using the inverse-KM method and shown with 95% confidence intervals. The change in testosterone levels from baseline to cycle 4 will be shown graphically using box-plots and reported with mean and standard deviation.

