2.2 Secondary Objectives

1. To evaluate the absolute PSA nadir as a result of treatment which is expressed for each subject in the absolute value and as a percentage, change from baseline.
2. To determine the time to PSA nadir from the start of treatment. which is the lowest PSA on treatment.
3. To determine the time to next subsequent antineoplastic therapy.
4. To determine the effect of investigational treatment on testosterone levels which is assessed by the change of testosterone from baseline to cycle 4.
5. To determine the safety and toxicities of the study drug as assessed by CTCAE version 5.

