2.5 Secondary Endpoint(s)

1. Absolute PSA nadir.
2. Time to PSA nadir.
3. Time to next subsequent antineoplastic therapy.
4. Effect of investigational treatment on testosterone levels.
5. Safety and toxicities of the study drug.

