4.5 Eligibility Confirmation

Study staff must adhere to MCWCC CTO SOPs regarding eligibility review/confirmation.

No waivers of protocol eligibility will be granted. When clinical factors relating to an eligibility item are unclear or questionable, the MCW PI can only provide guidance or clarification on eligibility. Any eligibility questions should be directed to [name] at [contact].

Inclusion Criteria

1. Patients aged \geq 18 years.
2. Histologically or cytologically confirmed prostate adenocarcinoma.
3. Prior radical prostatectomy or definitive radiation.
4. Biochemically recurrent prostate cancer with PSA doubling time \leq 9 months at the time of study entry (calculated per MSKCC prostate nomogram: https://www.mskcc.org/nomograms/prostate/psa_doubling_time). Calculation of PSA doubling time should include the use of all available PSA values obtained within the past 12 months prior to randomization, with a minimum of three values separated by at least two weeks apart. The PSA values used to calculate the PSA doubling time must all be \geq 0.1 ng/mL and should be measured in the same laboratory whenever feasible.
5. Prior adjuvant or salvage radiation or not a candidate for radiation based upon clinical assessment of disease characteristics and patient comorbidities. (N/A for patients who underwent definitive radiation therapy).
6. Screening PSA $>$ 0.5 ng/mL.
7. No definitive evidence of metastases on screening imaging per the judgment of the investigator. Pelvic lymph nodes measuring 1.5 cm or less in short axis diameter are allowed. Lesions identified on imaging modalities (e.g. PSMA or choline PET) that are not visualized on CT and/or MRI or radionuclide bone scan are allowed. Equivocal lesions on bone scan should be followed up with additional imaging as clinically indicated.
8. Screening serum testosterone $>$ 50 ng/dL.
9. Eastern Cooperative Oncology Group (ECOG), Performance Status grade 0-1 or Karnofsky Performance Status \geq 70.
10. No prior JAK2 inhibitor treatment.
11. Male patients, even if surgically sterilized (i.e., status post-vasectomy), must agree to one of the following:
 - Practice effective barrier contraception and another effective method of birth control if he is having sex with a woman of childbearing potential during the entire study period and through 90 calendar days after the last dose of study agent
12. Ability to understand a written informed consent document, and the willingness to sign it.

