4.6 Discontinuation of Study Treatment, Withdrawal, and Compliance

Treatment duration is 2 years. Patients may continue drug beyond two years if, in the opinion of the treating physician, the patient is benefitting from treatment and benefits outweigh any risks of therapy

Discontinuation from the study treatment does not mean discontinuation from the study. The subject will be considered in follow-up, study procedures should still be completed as indicated by the study protocol, and AEs/SAEs will continue to be reported according to this protocol.

In the absence of treatment delays due to adverse events, study treatment/intervention may continue until:

- Disease progression per PCWG3 guidelines
- General or specific changes in the subject's condition renders the subject unacceptable for further treatment in the investigator's judgment.
- An inter-current illness that prevents further treatment administration.
- The subject decides to withdraw from the study.
- The subject has significant noncompliance with the protocol (see below).
- Unacceptable adverse event(s) and/or dose level reduction beyond requirements as detailed in this protocol.
- The clinical need for concomitant therapy that is not permitted in the study.
- Subjects who sign the informed consent form, enroll and receive the study intervention, but subsequently withdraw, or are withdrawn or discontinued from the study will not be replaced.

Progression of disease

Progression of disease per PCWG3 is defined as one or more of the following:

PSA progression

Recognize that a favorable effect on PSA may be delayed for \geq 12 weeks, even for a cytotoxic drug. Monitor PSA by cycle but plan to continue through early rises for a minimum of 12 weeks unless other evidence of progression.

If there is a decline in PSA from baseline: record time from baseline to the first PSA increase that is $\geq 25\%$ and ≥ 2 ng/mL above the nadir, and which is confirmed by a second value ≥ 3 weeks later (i.e., a confirmed rising trend).

If there is no decline in PSA from baseline but stable PSA at 12 weeks: PSA progression will be defined as $\geq 25\%$ and ≥ 2 ng/mL from PSA at 12 weeks .

Radiographic progression

Radiographic progression will be assessed per RECIST 1.1. Any new unequivocal bone lesion is considered progression, except if that lesion appears in the first post-treatment scan; in that

case, document the event, continue treatment until two additional new lesions appear, and record both events.

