8.8 Other analyses

Demographic and clinical characteristics of the patient population will be reported using appropriate descriptive statistics such as frequencies and percentages with standard errors for categorical variables, mean with standard error or median with quartiles for continuous variables. The disposition of each subject will be reported as a listing.

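### PSA nadir is to be summarised only by mean and SD; absolute nadir is likely right-skewed, so median, quartiles and a per-patient plot should be added (minor, descriptive)

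*Combined protocol and SAP*

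**What the plan says.** Section 8.5 fixes the summary of this endpoint in one sentence: "The PSA nadir values will be summarized with mean and standard deviation as absolute values and as percent change from baseline PSA value". Section 2.2 has nadir reported on both scales and identifies it in the next objective: "which is the lowest PSA on treatment". Section 2.5 lists it first of five secondary endpoints, with no ranking, test or threshold.

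No other sentence gives nadir a robust or graphical summary:

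- The median in 8.5 belongs to time to nadir and time to next therapy.
- The box-plots in 8.5 are for testosterone change.
- The medians in 8.6 are for geriatric assessment scores.
- Section 8.8 allows "mean with standard error or median with quartiles for continuous variables", but only for demographic and clinical characteristics.

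The eligibility criteria require a screening PSA above 0.5 ng/mL and a doubling time of at most 9 months. They set no upper limit on PSA and no lower limit on doubling time.

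**The concern.** Absolute PSA in this population is bounded below and open above. If a few men enter with PSA far above the rest and do not respond deeply, their nadirs pull the mean away from the typical man, and the SD mostly records how extreme those few are. A reader given only those two numbers cannot recover where most men lie.

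The risk is greatest if the trial stops early. Section 8.3 gives a 38% to 45% chance of stopping at the interim when the true median is six months. Only 10 men are then guaranteed. If accrual continues at the assumed 1.5 per month during the tenth man's six months, the number is about 10 + 1.5 × 6 = 19. Descriptive PSA results would then be much of what the trial can report.

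The plan is also uneven: testosterone gets a box-plot and geriatric scores get a median, while PSA nadir gets neither.

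**Working it through.** The plan states no mean, SD or distribution for PSA nadir, so there is no figure of its own to reproduce. The check asks how far mean and SD can drift from the typical value.

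**Inputs from the documents.** n = 46, or 10 at the interim (8.3); screening PSA above 0.5 ng/mL with no upper limit, and doubling time at most 9 months (4.5); nadir is the lowest value on treatment (2.2).

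**Assumptions, not in the documents.** Absolute nadir is log-normal with log-SD s from 0.8 to 1.5; a typical nadir is 3 ng/mL and a high one 100 ng/mL; a typical percent change is -40%; the first on-treatment PSA comes at about 4 weeks (28/30.4 months). The study calendar is too damaged in the text to confirm the last.

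**1. Absolute nadir, theory.** Mean/median = exp(s²/2); SD/mean = √(exp(s²) − 1).

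- s = 0.8: 1.38 and 0.95
- s = 1.0: 1.65 and 1.31
- s = 1.5: 3.08 and 2.91

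**2. Absolute nadir, simulated trials of 46 men (40,000 per setting).**

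| s | typical sample mean/median | trials with SD > mean | CV of the mean | CV of the geometric mean |
|---|---|---|---|---|
| 0.8 | 1.35 | 21% | 14% | 12% |
| 1.0 | 1.6 | about 67% | 19% | 15% |
| 1.5 | 2.8 | over 99% | 42% | 22% |

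Flooring the values at one-sixth of the median (0.5 against 3 ng/mL) leaves the mean/median ratios and the share of trials with SD above the mean essentially unchanged.

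**3. Absolute nadir, hand examples (the rest at 3 ng/mL).**

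- n = 46, one man at 100: mean (45 × 3 + 100)/46 = 5.1, SD 14.3, median 3.
- n = 46, three men at 100: mean (43 × 3 + 300)/46 = 9.3, SD 24.2, median 3.
- n = 10, one man at 100: mean (9 × 3 + 100)/10 = 12.7, SD 30.7, median 3.

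**4. Percent change.** A man whose PSA only rises has his nadir at his first on-treatment value. With no drug effect and doubling time DT in months, that value is u = 100 × (2^(t/DT) − 1). At t = 28/30.4:

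- DT 9 months: +7.4%
- DT 3 months: +23.7%
- DT 1 month: +89.3%

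With k such men and the rest at -40%, the mean shifts by k(40 + u)/n points while the median stays at -40%.

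- n = 46, k = 1: from 47.4/46 = 1.0 to 129.3/46 = 2.8 points.
- n = 46, k = 3: from 3 × 47.4/46 = 3.1 to 3 × 129.3/46 = 8.4 points, giving means of -36.9% to -31.6%.
- n = 10, k = 1: from 4.7 to 12.9 points.
- n = 10, k = 3: from 14.2 to 38.8 points, giving means of -25.8% to -1.2%.

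If baseline counts as a candidate for the nadir, u = 0 and the shifts fall to 40k/n: 0.9 to 2.6 points at n = 46, and 4 to 12 at n = 10.

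**The case against.** The strongest reply is that little depends on this. Nadir is descriptive, carries no test or decision rule, and the go/no-go rests on six-month PSA-progression-free survival. A correctly computed mean is not wrong, an SD larger than its mean itself warns of skew, and nothing forbids adding medians later. Percent change, which removes differences in baseline level, is already planned. The log-SD range is assumed. All of this stands, and it is why the point is minor. It does not close the gap: the warning does not tell the reader where the typical man lies, and the summary is better fixed before the data are seen.

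A reader might also infer something stronger: that men with large PSA rises would make the mean percent change positive although most men declined. The documents do not support that. The endpoint is the lowest value on treatment, not the peak or the last value, and section 4.6 has PSA followed closely: "Monitor PSA by cycle but plan to continue through early rises for a minimum of 12 weeks". With 45 men at -40%, one man would need a nadir above 45 × 40 = +1800% to turn the mean positive, which at a first PSA on day 28 implies a doubling time of about 7 days. Even at n = 10 he would need more than 9 × 40 = +360%, a doubling time of about 13 days. Nor is right skew of percent change established: if most men change little and a few respond deeply, it is left-skewed.

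**Conclusion.** The point holds for absolute nadir, as a minor reporting weakness. Mean and SD are its only planned summaries. With no upper limit on entry PSA, a few men may dominate them: at n = 46 the mean is typically about 1.35 to 2.8 times the median under an assumed log-SD of 0.8 to 1.5, and a single extreme value weighs more at n = 10. The true size depends on a PSA distribution that the documents do not give, so they do not show that the summary will mislead, only that it may.

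For percent change the effect is small at full enrolment, about 1 to 8 points for one to three men with only rising PSA. It becomes large only near n = 10 with several such men or very short doubling times. A reader might also take nadir to be the trial's main activity measure after the primary endpoint; section 2.5 lists it first but gives it no such rank. The primary analysis and both stage decisions are unaffected.

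**What to change.** Rewrite the nadir sentence in 8.5 so that absolute nadir and percent change are each reported as median, quartiles and range. Add a per-patient waterfall plot of percent change, and the geometric mean ratio of nadir to baseline (computed on the log scale) with its 95% CI. Mean and SD may remain as extra columns. The same sentence can say whether the baseline value counts towards the nadir, since that decides whether a man with only rising PSA is recorded at 0% or above.

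The cost is a sentence or two and one plot. It needs no new data and changes neither the sample size nor the primary or interim analysis.

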1 BACKGROUND

1.1. Prostate cancer

Prostate cancer (PC) is the most common non-cutaneous malignancy among elderly men, with more than 60% of all PC cases diagnosed in men over 65 years of age. (1) The estimated prevalence of PC in men aged 75 years and older is currently more than a million and expected to quadruple by 2030, given the long natural history of the disease and aging of the population. (2, 3) Systemic disease from prostate cancer includes biochemical recurrence (a rise in PSA after definitive treatment with no radiographic evidence of disease elsewhere), as well as overt metastatic disease confirmed by imaging. Once the disease is systemic, the goal of treatments is palliative, and physicians should take into account therapy-related side effects, which can adversely affect the quality of life.

Recurrent PC with a short PSA doubling time (≤ 9 months) represents a high-risk subpopulation with a significant risk of PC-related mortality. The median PC-specific survival for patients with rapidly rising serum PSA is approximately five years, which is comparable to patients with limited metastatic castration-sensitive disease (< 4 bone metastases and/or node-only soft tissue involvement).

Intermittent androgen deprivation therapy (ADT) achieved with GnRH agonist or antagonist is considered the standard of care for biochemical relapse. Side effects of ADT include but are not limited to weakness, osteoporosis, muscle wasting, metabolic syndrome, hot flashes, increased risk of diabetes, cardiovascular disease, depression, impotence, falls, and cognitive/mood disorders. (4-7) While these untoward effects are tolerable in the young fit population, they lower the quality of life significantly. Importantly, they can have significant adverse consequences in elderly cancer patients with preexisting comorbidities and functional impairment. (5, 7, 8) Once ADT is initiated for systemic disease, it is usually continued for life.

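### PSA change is summarised only by the single lowest unconfirmed on-treatment value, which understates PSA growth and leaves small declines uninterpretable in a single-arm trial

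*Combined protocol and SAP*

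**What the plan says.** The first objective in section 2.2 is "To evaluate the absolute PSA nadir as a result of treatment", expressed per subject as an absolute value and as a percent change from baseline. The second objective, on time to nadir, defines the nadir: "which is the lowest PSA on treatment". The planned analysis in section 8.5 is a mean and standard deviation of the nadir values, "as absolute values and as percent change from baseline PSA value".

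The following is not specified:
- whether a low value must be repeated before it counts;
- a time window for the nadir;
- whether baseline is the screening PSA or the Cycle 1 Day 1 PSA;
- any PSA change at a fixed visit. Section 8.5 does plan a baseline-to-cycle-4 change, but for testosterone only.

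Section 4.6 is stricter about rises. In men whose PSA first fell, a rise counts only if it is one "which is confirmed by a second value" at least 3 weeks later. The trial has a single arm (section 3.1). Eligibility (section 4.5, Eligibility Confirmation) requires "Biochemically recurrent prostate cancer with PSA doubling time" of at most 9 months, so PSA is rising at entry.

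**The concern.** The nadir percent change compares the minimum of several noisy values, each man's taken at a different time, with one noisy baseline value. Two effects push it downward. In a man whose PSA only rises, the minimum is usually one of the first draws, so growth after that is discarded. Measurement and biological noise then lowers the minimum further and can take it below baseline. Replacing the mean by a median cures neither effect.

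Section 2.2 presents the nadir as a consequence of treatment, and there is no control arm to show what the same statistic would be without the drug. It is also the only planned summary of the size of PSA change. A small mean rise, or some men slightly below baseline, could therefore be read as slowed PSA growth when PSA was still growing at its entry rate.

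**Working it through.** The documents state no figure for the nadir, so there is nothing of the plan's own to reproduce. The check asks what the planned statistic would show under an inert drug.

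**Inputs**
- Doubling time (DT): at most 9 months (sections 1.1 and 4.5). No distribution is given, so 2 to 9 months is an assumed range.
- PSA schedule: section 4.6 says "Monitor PSA by cycle but plan to continue through early rises for a minimum of 12 weeks", and the Study Calendar has 28-day cycles. Six post-baseline draws were used at weeks 4, 8, 12, 16, 20 and 24. Moving the last to day 196, for two-monthly visits, changes the results little.
- Within-man CV of PSA: not in the documents. Assumed 5% to 20%.
- Baseline: assumed to be Cycle 1 Day 1.

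**Step 1: no noise.** True PSA ratio at day t = 2^(t / (30.4375 × DT)). For a rising series the minimum is the first draw, at day 28.
- DT 9 months: week 4 is 2^(28/273.9) = 1.073; week 12 is 2^(84/273.9) = 1.237.
- DT 6 months: 2^(28/182.6) = 1.112; 2^(84/182.6) = 1.376.
- DT 3 months: 2^(28/91.3) = 1.237; 2^(84/91.3) = 1.892.
- DT 2 months: 2^(28/60.9) = 1.376; 2^(84/60.9) = 2.602.

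Even with a perfect assay, the nadir shows only 7.3/23.7 = 31% of the week-12 growth at 9 months and 37.6/160.2 = 23% at 2 months. This part does not depend on the assumed CV.

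**Step 2: with noise.** Independent log-normal noise was applied to baseline and to each draw; nadir change = min(y1,…,y6)/y0 − 1, with at least 200,000 simulated men per setting.

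| DT (months) | True week-12 change | Mean nadir change, CV 5% to 20% | Share with nadir below baseline, CV 5 / 10 / 15 / 20% |
|---|---|---|---|
| 9 | +24% | about +7% to -3% | 17 / 39 / 51 / 59% |
| 6 | +38% | about +11% to +4% | 7 / 26 / 39 / 47% |
| 4.5 | +53% | about +15% to +11% | 2 / 17 / 29 / 39% |
| 3 | +89% | about +23% to +24% | 0.1 / 7 / 17 / 26% |
| 2 | +160% | about +38% to +40% | 0 / 1 / 7 / 14% |
| Even mix 2-9 | +54% | +15% to +10% | 6 / 21 / 33 / 42% |

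The median behaves alike: at DT 9 months and CV 10 / 15 / 20% it is +3.8 / -0.3 / -4.9%.

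**Step 3: size of false falls.** At CV up to 20%, a nadir at least 30% below baseline occurs in at most 11% of men, and at least 50% below in at most about 0.6%.

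**Step 4: effect of the baseline choice.** For DT 6-9 months and CV 10-20%, the share below baseline is 26-59%. If baseline is a screening value 28 days earlier, it is 7-47%. The undefined baseline therefore matters.

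**Step 5: alternatives, same band (DT 6-9 months, CV 10-20%).** Requiring two consecutive values below baseline lowers the share to 4-25%. Pairing the lowest value with the next one is at least as strict, so it cannot exceed that. A fixed week-12 change gives about 1-22%.

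**The case against.** The strongest reply is that the nadir is a descriptive secondary endpoint with no test, threshold or success criterion. PSA growth is judged by six-month PSA-progression-free survival, and both decision rules (sections 8.3 and 8.9) use only that. This stands. A reader might infer that the trial could declare PSA control that never happened; the documents do not support that.

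A reader might also infer that a quarter to more than half of men would show a decline on an inert drug. That range needs doubling times of 6-9 months, at the slow-growing end of eligibility, and an assumed CV of 10-20%. Moreover, section 8.5 plans a mean and SD, not a proportion with decline, and the mean under an inert drug is a rise in nearly every setting above. It turns negative only at 9 months with CV 20%.

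Nor does it follow that the nadir can never be read as a treatment effect: noise produces small dips, not halvings. Simulating a truly flat PSA would give many more apparent declines, but a flat PSA is not what an inert drug would produce in men selected for rapid doubling.

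Finally, section 4.6 warns that a PSA benefit may take 12 weeks or longer to appear. Replacing the nadir by a week-12 change as the lead summary could therefore miss a late effect, so week 12 should be supportive and later visits shown too.

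What survives is the loss of growth information, which Step 1 shows without any CV assumption, and the ambiguity of small declines.

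**Conclusion.** The concern holds in limited form. As planned, the only summary of PSA change discards most of the week-12 growth at every doubling time examined, and a small mean rise or small individual declines cannot be interpreted as an effect of treatment.

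At 6 months and CV 10%, an inert drug would be reported with a mean nadir change of about +10% while true PSA had risen 38% by week 12. The frequency of false declines is much less certain: about 0% (2 months, CV 5%) to 59% (9 months, CV 20%), or 6-42% for an even mix of 2-9 months. It rests on an assumed CV, an assumed spread of doubling times, independent noise and a Cycle 1 Day 1 baseline. Large falls remain informative, and the primary endpoint and its decision rules are not affected.

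**What to change.** In section 8.5:
1. Keep the nadir summary and state that baseline is the Cycle 1 Day 1 PSA.
2. Add, as a supportive summary, the percent change from baseline to Cycle 4 Day 1 (week 12), the cycle already used for testosterone. Show later scheduled visits such as Cycle 6 beside it, because of the delayed effect described in section 4.6.
3. Beside the raw nadir, report a confirmed nadir: the higher of the lowest value and the next PSA at least 3 weeks later. That is the interval section 4.6 already uses for rises.
4. State that small unconfirmed declines will not be interpreted as a result of treatment.

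The cost is a wording change and one extra table from PSA values already scheduled; no visit or treatment rule changes. The downsides are that the confirmed nadir will look less favourable than the raw one, men without a Cycle 4 value are missing from the week-12 summary, and a nadir at the last draw cannot be confirmed and should be counted as such.

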8 STATISTICAL CONSIDERATIONS

8.1 Study Populations

Efficacy population — all enrolled subjects who received at least one dose of the study drug and have either died or have at least one evaluation of PSA after the initiation of study treatment.

Safety population — all enrolled subjects who received at least one dose of the study drug.

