8.10 Missing data

For all outcomes, summary statistics will include the count of missing and non-missing values. Patients with missing value for the primary outcome, PFS, will be censored at the time when last known to be alive and without progression. A similar approach will be used for other time-to-event outcomes, such as time to PSA nadir. Secondary outcomes requiring numeric values, such as geriatric assessments, PSA and testosterone levels will be analyzed among patients with non-missing values as required for each analysis (e.g., non-missing value at specific time point for cross-sectional analysis, and non-missing values at two time points for change analyses). The limitations of extensive missingness, if present, will be clearly noted in all reports and any related findings will be interpreted with caution.

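### Time to PSA nadir goes into a Kaplan-Meier median with no rule for men whose PSA does not fall, so the median mixes non-response with fast response

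*Combined protocol and SAP*

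**What the plan says.** The objective in Section 2.2 reads: "To determine the time to PSA nadir from the start of treatment. which is the lowest PSA on treatment". A fall below baseline is not part of the definition.

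Section 8.5 gives the analysis: "The time to PSA nadir and time to subsequent antineoplastic therapy will be summarized using Kaplan-Meier (KM) curves". It continues: "The median will be estimated using the inverse-KM method and shown with 95% confidence intervals". The preceding sentence of 8.5 summarises the nadir value itself by mean and standard deviation, as an absolute value and as percent change from baseline.

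Section 8.10 censors men with a missing primary outcome at the time last known alive and progression-free, and adds: "A similar approach will be used for other time-to-event outcomes, such as time to PSA nadir". It does not say when a nadir counts as missing.

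Section 8.5 names no population. The efficacy population in Section 8.1 is "all enrolled subjects who received at least one dose of the study drug and have either died or have at least one evaluation of PSA" (taken once treatment has begun), so it contains no decliner subset.

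Section 4.6 expects men without a decline and gives them their own progression rule: "If there is no decline in PSA from baseline but stable PSA at 12 weeks". It also keeps men on treatment through early rises: "Monitor PSA by cycle but plan to continue through early rises for a minimum of 12 weeks unless other evidence of progression".

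**The concern.** A lowest on-treatment value exists for every man with at least one on-treatment PSA. If his PSA rises at each visit, that value is his first, and nothing in Section 8.10 makes it missing. Followed as written, the plan counts him as an early event. A man with a rapid deep response can have his event at the same visit, while a slow responder has his much later. Short times therefore carry two opposite meanings.

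The situation is foreseeable. Entry requires "Biochemically recurrent prostate cancer with PSA doubling time" of 9 months or less, so PSA is rising in every man at baseline, and there is no control arm against which to calibrate the median. At stake is whether one named secondary endpoint can be read. The primary analysis, the futility rule and the sample size are not affected.

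**Working it through.** The documents state no expected median, decline rate or precision for this endpoint, so there is no figure to reproduce. Two checks were made.

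**Inputs from the documents.** Up to 46 men, single arm (Sections 3.1, 8.3). Doubling time 9 months or less (Section 4.5, Eligibility Confirmation). PSA by 28-day cycle, then every 2 months from Cycle 6 (Study Calendar). On-treatment visits are taken as weeks 4, 8, 12, 16, 20, then every 8 weeks. The calendar places Day 1 assessments before the first dose, so the first on-treatment PSA is read as week 4.

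**Assumptions, not in the documents.** The share without decline, the timing of nadir in decliners, and 10% measurement noise.

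**1. Mixture calculation.** Let a share q of men only rise (nadir at week 4). Let decliners follow a Weibull distribution with shape 1.5 and median m weeks: F(t) = 1 − exp(−0.693 × (t/m)^1.5). The all-men median is the first visit t with q + (1 − q)F(t) ≥ 0.5, that is, F(t) ≥ (0.5 − q)/(1 − q).

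Example with m = 20 and q = 0.4: the required F is 0.1/0.6 = 0.167. F(8) = 1 − exp(−0.693 × 0.253) = 0.161 is too small and F(12) = 1 − exp(−0.693 × 0.465) = 0.275 is enough, so the median is 12 weeks.

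| Share only rising | F needed | m = 12 | m = 20 | m = 36 |
|---|---|---|---|---|
| 0% | 0.500 | 12 wk | 20 wk | 36 wk |
| 20% | 0.375 | 12 wk | 16 wk | 28 wk |
| 30% | 0.286 | 8 wk | 16 wk | 28 wk |
| 40% | 0.167 | 8 wk | 12 wk | 16 wk |
| 50% or more | 0 or less | 4 wk | 4 wk | 4 wk |

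The median among decliners stays at 12, 20 or 36 weeks down each column, by construction. At q = 0.5 or above the all-men median is the first visit whatever m is.

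**2. Simulated PSA courses.** 46 men per trial, 300 trials per scenario, 10% noise, nadir taken up to PSA progression. The table shows the mean of the trial medians.

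| Scenario | Post-baseline values only | Day 1 value allowed |
|---|---|---|
| Inert drug, doubling time 9 months | 4.2 wk | 0.2 wk |
| Inert drug, doubling time 5 months | 4.0 wk | 0 wk |
| 50% fall by week 4 in every man | 4.2 wk | 4.2 wk |
| 50% fall by week 20 in every man | 20 wk | 20 wk |

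If the slow drug works in only 30%, 50% or 70% of men, the post-baseline figure is 7.2, 13.7 or 19.6 weeks. These lie above the 4-week floor of the first check because noise shifts some non-decliners' lowest value to a later visit. The median still moves with the share who respond, although the speed of response is unchanged.

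**3. Would any fall below baseline serve to define a decliner?** At a doubling time of 9 months, PSA grows over 4 weeks by a factor of 2^(4/(9 × 4.345)) = 1.07. The noise on a ratio of two values is about 0.10 × √2 = 14%. Chance falls are therefore common. On an inert drug, with visits in weeks 4 to 28, about 20% (doubling time 5 months) to 39% (9 months) of men fall below baseline at least once, and their median time to nadir is again 4 weeks. A fall of 25% or more occurs in under 1%.

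**The case against.** Several points on the other side stand.

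- **The median is not reported alone.** Section 8.5 gives percent change at nadir for the same endpoint, and Section 8.4 gives the PSA-progression-free curve. An inert drug would show a mean nadir near or above baseline beside its short median. A reader might infer that the median carries no information or would pass as a fast effect; with those summaries alongside, the documents do not support that. But a mean and standard deviation do not give the share who declined, so they do not decode the median.
- **Men without decline do not always have the shortest times.** That is exact only for a PSA that rises at every visit. With 10% noise, about 22% (doubling time 5 months) to 43% (9 months) of inert-drug men who never fall below baseline have their lowest value after week 4. This adds ambiguity and does not repair the median.
- **Inclusion of all men is inferred.** It follows from the absence of any restriction in Sections 8.1, 8.5 and 8.10; no sentence states it.
- **Men still falling at their last PSA** might be thought a separate flaw. They can be treated as ordinary censored cases, and 8.10 points towards censoring.
- **The size depends on assumptions.** With half the men declining, the 2.5–97.5% range of the estimated median is 1 to 5 months if decliners reach nadir in months 4 to 9, but 1 to 3 months if they may do so from month 1.

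**Conclusion.** The point holds in a limited form. As written, the plan puts the lowest on-treatment PSA into a Kaplan-Meier median with neither a restriction to men whose PSA falls nor a rule for those whose PSA does not. With post-baseline values only, an inert drug and a drug acting fully by week 4 both give about 4 weeks. If half or more of the men only rise, the median is the first PSA visit.

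Below that share the distortion is graded: with an assumed decliner median of 20 weeks, 16 weeks at 20–30% without decline and 12 weeks at 40%. The true share is not in the documents, so the size in this trial cannot be stated. The endpoint is untested and descriptive, and no decision depends on it. This is a cheap improvement to a secondary summary and does not threaten the trial's conclusion.

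**What to change.** In Sections 8.5 and 8.10:

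- Report the number and proportion of men whose PSA falls from baseline by at least a prespecified amount beyond assay noise, or whose fall is confirmed by a second value. Any fall at all is too loose a criterion, as the third check shows.
- Summarise time to nadir descriptively among those men only, labelled as conditional on decline.
- State that only post-baseline values count (or that Day 1 may count), and flag or censor men whose lowest value is their last PSA.
- Keep Kaplan-Meier over all men for time to subsequent antineoplastic therapy.

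The cost is a few sentences, with no new data, visits or change to the sample size or primary analysis. The downside is that the summary covers a subset defined after baseline, so it is descriptive only and not an estimate of drug effect.
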